Has subject engaged in Non-Suicidal Self-Injurious Behavior? Interrupted Attempt: When the person is interrupted (by an outside circumstance) from starting the potentially self-injurious act (if not for that, actual attempt would have occurred). Overdose: Person has pills in hand but is stopped from ingesting. Once they ingest any pills, this becomes an attempt rather than an interrupted attempt. Shooting: Person has gun pointed toward self, gun is taken away by someone else, or is somehow prevented from pulling trigger. Once they pull the trigger, even if the gun fails to fire, it is an attempt. Jumping: Person is poised to jump, is grabbed and taken down from ledge. Hanging: Person has noose around neck but has not yet started to hang - is stopped from doing so. Has there been a time when you started to do something to end your life but someone or something stopped you before you actually did anything? If yes, describe:	Yes No   Total # of interrupted _____
Aborted Attempt: When person begins to take steps toward making a suicide attempt, but stops themselves before they actually have engaged in any self-destructive behavior. Examples are similar to interrupted attempts, except that the individual stops him/herself, instead of being stopped by something else. Has there been a time when you started to do something to try to end your life but you stopped yourself before you actually did anything? If yes, describe:	Yes No   Total # of aborted _____
Preparatory Acts or Behavior: Acts or preparation towards imminently making a suicide attempt. This can include anything beyond a verbalization or thought, such as assembling a specific method (e.g., buying pills, purchasing a gun) or preparing for one's death by suicide (e.g., giving things away, writing a suicide note). Have you taken any steps towards making a suicide attempt or preparing to kill yourself (such as collecting pills, getting a gun, giving valuables away or writing a suicide note)? If yes, describe:	Yes No  
Suicidal Behavior: Suicidal behavior was present during the assessment period?	Yes No  
Suicide:	Yes No  
Answer for Actual Attempts Only	Most Lethal Attempt Date:
Actual Lethality/Medical Damage: 0. No physical damage or very minor physical damage (e.g., surface scratches). 1. Minor physical damage (e.g., lethargic speech; first-degree burns; mild bleeding; sprains). 2. Moderate physical damage; medical attention needed (e.g., conscious but sleepy, somewhat responsive; second-degree burns; bleeding of major vessel). 3. Moderately severe physical damage, medical hospitalization and likely intensive care required (e.g., comatose with reflexes intact; third-degree burns less than 20% of body; extensive blood loss but can recover; major fractures). 4. Severe physical damage, medical hospitalization with intensive care required (e.g., comatose without reflexes; third-degree burns over 20% of body; extensive blood loss with unstable vital signs; major damage to a vital area). 5. Death	Enter Code _____
Potential Lethality: Only Answer if Actual Lethality=0 Likely lethality of actual attempt if no medical damage (the following examples, while having no actual medical damage, had potential for very serious lethality: put gun in mouth and pulled the trigger but gun fails to fire so no medical damage; laying on train tracks with oncoming train but pulled away before run over). 0 = Behavior not likely to result in injury 1 = Behavior likely to result in injury but not likely to cause death 2 = Behavior likely to result in death despite available medical care	Enter Code _____

11. DESCRIPTION OF GLOBAL AMENDMENT(S)

11.1 GLOBAL AMENDMENT 1

Date of amendment		14 March 2019
EudraCT number		2018-004806-24
EU number		
BI Trial number		1346-0029
BI Investigational Medicinal Product(s)		BI 425809
Title of protocol		A study to investigate the effects of donepezil on the pharmacokinetics of BI 425809 and vice versa in healthy male and female subjects (Open-label, two-treatment, two-period, one fixed sequence cross-over design)
To be implemented only after approval of the IRB / IEC / Competent Authorities		
To be implemented immediately in order to eliminate hazard – IRB / IEC / Competent Authority to be notified of change with request for approval		
Can be implemented without IRB / IEC / Competent Authority approval as changes involve logistical or administrative aspects only		
Section to be changed		
 1. Section 3.1 2. Section 3.3.2 3. Section 3.3.3 4. Section 3.3.4.1
Description of change		
 1. Details on trial conduct added 2. Inclusion criterion 5 was corrected: The requirement to use adequate contraception for at least 30 days prior first drug administration was removed. 3. Exclusion criterion 31 (Normal liver function tests, total bilirubin and creatinine at screening) added 4. Treatment discontinuation in case of elevated liver parameters changed from of “...AST and/or ALT \geq3-fold ULN AND an elevation of total bilirubin \geq2-fold ULN...” to “...AST and/or ALT \geq3-fold ULN OR an elevation of total bilirubin \geq2-fold ULN...”
Rationale for change		
 1. Based on the feedback by BfArM, the respective recommendations were included in a revised protocol. This applies for all changes except of the change in section 1.3.2.

	
2. The adaption of inclusion criterion 5 was based on EC feedback. EC raised concerns that the 30 days pre-administration period as part of the contraception methods starts before the subjects had consented to trial participation. However, the requirement to use adequate contraception for at least 30 days prior first drug administration is only needed for oral contraceptives as incorrect use may affect the contraceptive effect. Since in this trial oral hormonal contraceptives are not allowed and the other recommended measures, e.g. non-hormonal intra-uterine devices, are immediately effective, a 30 day pre-administration period for the allowed contraceptive methods is not applicable and was deleted.
 
In addition a typo in the Flow Chart of part 2 was deleted.

--	--

11.2 GLOBAL AMENDMENT 2

Date of amendment		13 May 2019
EudraCT number		2018-004806-24
EU number		
BI Trial number		1346-0029
BI Investigational Medicinal Product(s)		BI 425809
Title of protocol		A study to investigate the effects of donepezil on the pharmacokinetics of BI 425809 and vice versa in healthy male and female subjects (Open-label, two-treatment, two-period, one fixed sequence cross-over design)
To be implemented only after approval of the IRB / IEC / Competent Authorities		
To be implemented immediately in order to eliminate hazard – IRB / IEC / Competent Authority to be notified of change with request for approval		
Can be implemented without IRB / IEC / Competent Authority approval as changes involve logistical or administrative aspects only		
Section to be changed		
 1. Synopsis 2. Flow Chart 3. Section 5.2.5 4. Appendix 10.1
Description of change		
 1. Trial Clinical Monitor changed to Clinical Trial Leader 2. Alcohol breath test was added to footnote 15 3. Visit 3 was added to footnote B 4. The Screening Version of the C-SSRS was replaced by the Baseline/Screening Version of the C-SSRS
Rationale for change		
 1. The naming of the function was changed within BI 2. By mistake alcohol breath test as part of the drug screening procedure upon admission was not added. This was corrected 3. An inconsistency between Flow Chart and Footnote B in Section 5.2.5 was corrected 4. By mistake the wrong C-SSRS version for the screening assessment was included. This was corrected

2. LIST OF ABBREVIATIONS

Term	Definition / description
ADME	Absorption, Distribution, Metabolism and Excretion
AE	Adverse Event
AESI	Adverse event of special interest
ALT	Alanine aminotransferase
ANOVA	Analysis of variance
AST	Aspartate aminotransferase
AUC _{0-tz}	Area under the concentration-time curve of the analyte in plasma over the time interval from 0 to the last quantifiable data point
AUC _{0-∞}	Area under the concentration-time curve of the analyte in plasma over the time interval from 0 extrapolated to infinity
BI	Boehringer Ingelheim
BP	Blood pressure
C _{max}	Maximum measured concentration of the analyte in plasma
CTP	Clinical Trial Protocol
CTR	Clinical Trial Report
CV	Arithmetic coefficient of variation
C-SSRS	Columbia Suicidal Severity Rating scale
ECG	Electrocardiogram
gCV	geometric coefficient of variation
gMean	Geometric mean
ICH	International Conference On Harmonisation
IPD	Important protocol deviations
IQRMP	Integrated quality and risk management plan
MedDRA	Medical Dictionary For Regulatory Activities
PK	Pharmacokinetics
PKS	Pharmacokinetic parameter set
PR	Pulse rate
RAGe	Report appendix generator
SAE	Serious adverse event
SD	Standard Deviation
SOC	System Organ Class

Term	Definition / description
TS	Treated set
TSAP	Trial Statistical Analysis Plan
ULN	Upper limit of normal range

3. INTRODUCTION

As per ICH E9 (1) the purpose of this document is to provide a more technical and detailed elaboration of the principal features of the analysis described in the revised CTP, and to include detailed procedures for executing the statistical analysis of the primary variables and other data.

This TSAP assumes familiarity with the CTP and its amendments. In particular, the TSAP is based on the planned analysis specification as written in CTP Section 7 "Statistical Methods and Determination of Sample Size". Therefore, TSAP readers may consult the CTP for more background information on the study, e.g., on study objectives, study design and population, treatments, definition of measurements and variables, planning of sample size, randomisation.

Study data will be stored in a trial database within Medidata Rave system.

The statistical analyses will be performed within the validated working environment CARE, including SASTM (current Version 9.4, by SAS Institute Inc., Cary, NC, USA), and a number of SASTM-based tools (e.g., macros for the analyses of AE data or laboratory data; Report Appendix Generator system (RAGe) for compilation/formatting of the CTR appendices).

PK parameters will be calculated using Phoenix WinNonlinTM software (version Phoenix 6.3, Certara USA Inc., Princeton, NJ, USA).

4. CHANGES IN THE PLANNED ANALYSIS OF THE STUDY

All analyses described in this TSAP are in accordance with the statistical methods described in the revised CTP.

5. ENDPOINTS

5.1 PRIMARY ENDPOINTS

Primary endpoints are PK endpoints of BI 425809 (part 1) and donepezil (part 2), as defined in Section 2.1.2 of the CTP:

- *AUC_{0-∞} (area under the concentration-time curve of the analyte in plasma over the time interval from 0 extrapolated to infinity)*
- *C_{max} (maximum measured concentration of the analyte in plasma)*

5.2 SECONDARY ENDPOINTS

5.2.1 Key secondary endpoints

Not applicable.

5.2.2 Secondary endpoints

Secondary endpoints are PK endpoints of BI 425809 (part 1) and donepezil (part 2), as defined in Section 2.1.3 of the CTP:

- *AUC_{0-tz} (area under the concentration-time curve of the analyte in plasma over the time interval from 0 to the last quantifiable data point)*

5.3.2 Safety parameters

Safety and tolerability of BI 425809 will be assessed based on further safety parameters defined in Section 2.2.2.2 of the CTP:

- *Adverse events (including clinically relevant findings from the physical and neurological examination)*
- *Safety laboratory tests, including faecal occult blood test*
- *12-lead ECG*
- *Visual tests*
- *Vital signs (blood pressure, pulse rate)*
- *Suicidality assessment (C-SSRS, only part 2)*

5.4 OTHER VARIABLES

5.4.1 Demographic and other baseline characteristics

CTP: *At the screening visit, the medical examination will include documentation of subject information, informed consent, demographics including height and body weight, smoking and alcohol history, relevant medical history and concomitant therapy, review of inclusion and exclusion criteria, visual tests, C-SSRS assessment (only for Part 2), review of vital signs (BP, PR), 12-lead ECG, laboratory tests, and a physical examination (including a neurological examination consisting of Romberg and Unterberger test, assessment of gait, further tests as needed).*

Body mass index will be calculated as weight [kg] / height [m]².

5.4.2 Treatment compliance and treatment exposure

Treatment compliance will not be analysed as a specific endpoint, cf. Section 4.3 of the CTP.

Treatment exposure is defined as the total dose and number of doses of BI 425809 and donepezil per subject.

6. GENERAL ANALYSIS DEFINITIONS

6.1 TREATMENTS

For basic study information on treatments to be administered, assignment of treatment groups, and selection of doses, cf. Section 4 of the CTP.

Each subject is planned to be treated in two subsequent treatment periods in a fixed sequence order. There will be no washout-period between the two treatment periods.

Part 1:

All subjects will receive a single dose of BI 425809 alone in Visit 2 and a single dose of BI 425809 after multiple dosing of donepezil in Visit 3.

Table 6.1: 1 Dosage and treatment schedule part 1

Treatment	Substance	Formulation	Unit strength	Dosage	Total dose
A (Reference 1)	BI 425809	Tablet	25 mg	1 tablet (Day 1, Visit 2)	25 mg
B (Test 1)	Donepezil	Tablet	5 mg	1 tablet (Day 1-7, Visit 3) q.d. 2 tablets (Day 8-28, Visit 3) q.d.	245 mg
	BI 425809	Tablet	25 mg	1 tablet (Day 22, Visit 3)	25 mg

Part 2:

All subjects will receive a single dose of donepezil alone in Visit 2 and then a single dose of donepezil after multiple dosing of BI 425809 in Visit 3.

Table 6.1: 2 Dosage and treatment schedule part 2

Treatment	Substance	Formulation	Unit strength	Dosage	Total dose
C (Reference 2)	Donepezil	Tablet	5 mg	2 tablets (Day 1, Visit 2)	10 mg
D (Test 2)	BI 425809	Tablet	25 mg	1 tablet (Day 1-24, Visit 3) q.d.	600 mg
	Donepezil	Tablet	5 mg	2 tablets (Day 10, Visit 3)	10 mg

For statistical analyses of AEs, vital signs, safety laboratory data and visual tests the following separate analysis phases will be defined for each subject:

Table 6.1: 3 Analysis phases for statistical analysis of AEs, vital signs, safety laboratory data and visual tests, part 1

Study analysis phase	Label	Start	End
Screening	Screening part 1	Date of informed consent	Date/time of first administration of BI 425809
On treatment BI 425809	BI part 1	Date/time of first administration of BI 425809	Date/time of first administration of donepezil
On treatment donepezil	Don part 1	Combination of two phases: First phase: Date/time of first administration of BI 425809 + 11*24h (i.e. REP of BI425809 of 11 days) Second phase: Date/time of second administration of BI 425809 + 11*24h (i.e. REP of BI425809 of 11 days)	Combination of two phases: First phase: Date/time of second administration of BI 425809 Second phase: Date/time of last administration of donepezil + 15*24h (i.e. REP of donepezil of 15 days) or 00:00 a.m. on day after subject's trial termination date whatever occurs earlier
On treatment BI 425809+ donepezil	Don + BI part 1	Combination of two phases: First phase: Date/time of first administration of donepezil Second phase: Date/time of second administration of BI 425809	Combination of two phases: First phase: Date/time of first administration of BI 425809 + 11*24h (i.e. REP of BI425809 of 11 days) Second phase: Date/time of second administration of BI 425809 + 11*24h (i.e. REP of BI425809 of 11 days)
Follow-up	F/U part 1	Date/time of last administration of donepezil + 15*24h (i.e. REP of donepezil of 15 days)	00:00 a.m. on day after subject's trial termination date

The planned duration of the analysis phase of BI part 1 is 8 days, of Don part 1 it is 28 days and of Don + BI part 1 it is 14 days.

Table 6.1: 4 Analysis phases for statistical analysis of AEs, vital signs, safety laboratory data and visual tests, part 2

Study analysis phase	Label	Start	End
Screening	Screening part 2	Date of informed consent	Date/time of first administration of Donepezil
On treatment donepezil	Don part 2	Date/time of first administration of donepezil	Date/time of first administration of donepezil + 15*24h (i.e. REP of donepezil of 15 days)
On treatment BI 425809	BI part 2	Combination of two phases: First phase: Date/time of first administration of BI 425809 Second phase: Date/time of second administration of donepezil + 15*24h (i.e. REP of donepezil of 15 days)	Combination of two phases: First phase: Date/time of second administration of donepezil Second phase: Date/time of last administration of BI 425809 + 11*24h (i.e. REP of BI 425809 of 11 days) or 00:00 a.m. on day after subject's trial termination date whatever occurs earlier
On treatment BI 425809+ donepezil	BI + Don part 2	Date/time of second administration of donepezil	Date/time of second administration of donepezil + 15*24h (i.e. REP of donepezil of 15 days)
Follow-up	F/U part 2	Combination of two phases: First phase: Date/time of first administration of donepezil + 15*24h (i.e. REP of donepezil of 15 days) Second phase: Date/time of last administration of BI 425809 + 11*24h (i.e. REP of BI 425809 of 11 days)	Combination of two phases: First phase: Date/time of first administration of BI 425809 Second phase: 00:00 a.m. on day after subject's trial termination date

The planned duration of the analysis phase of Don part 2 is 15 days, of BI part 2 it is 19 days and of BI + Don part 2 it is 15 days.

AE displays in CTR Section 15.3, Appendix 16.1.13.1.8.2 and Appendix 16.1.13.1.8.3 will present results for the on-treatment phase only.

In AE tables in CTR Section 15.3 (but not in Appendix 16.1.13.1.8.2 and Appendix 16.1.13.1.8.3 AE tables), the following total will be provided in addition:

- "**Total on-trt part x**", defined as the total over all on-treatment phases, x will be replaced with 1 or 2 for the respective part
- "**Total BI part x**", defined as the total over all on-treatment phases involving BI, x will be replaced with 1 or 2 for the respective part

CTR Appendix 16.1.13.1.8.1 displays will present results for the screening, on-treatment and follow-up phases.

Additionally to the total defined above, the following total will be provided in AE tables in CTR Section 16.1.13.1.8.1:

- **"Total part x"**, defined as the total over all study phases (screening + on-treatment + follow-up) , x will be replaced with 1 or 2 for the respective part

More details on the technical implementation of these analyses are provided in the ADS Plan of this TSAP.

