13. Colour discrimination, visual acuity testing, Amsler grid test: tests will be performed at screening, EOT and at any time visual adverse events are reported
14. All blood pressure measurements, as well as pulse rate and ECG will be measured after at least 5 minutes of rest in the supine position
15. Only urine drug screening and alcohol breath test and urine pregnancy testing in females
16. Bed rest (except going to the toilet)

* There is no wash-out period between Visit 2 and Visit 3. Day 1 of Visit 3 follows directly after day 8 of Visit 2 but these are different days

Part 2

Visit**	Day	Planned time (relative to first drug administration [h:min])	Approximate clock time of actual day [h:min]	Event and comment	Safety laboratory	PK _{plasma} (BI 425809)	PK _{plasma} Donepezil	Safety assessments	12-lead ECG ¹⁴	Vital signs (BP, PR) ¹⁴	Questioning for AEs and concomitant therapy ⁶	
1	-21 to -1	n.a.	n.a.	Screening ¹	X ⁵			X ^{9,10,13}	X	X		
2 (Treatment C)	-3 to -1	-24:00	n.a.	Ambulatory visit	X ¹²						X	
	-1	-12:00	20:00	Admission to trial site	X ¹⁵						X	
	1	-02:00	06:00			X ²	X ²	X ^{10,2}	X ²	X ²	X ^{2,7}	
		00:00	08:00	Drug administration, 10 mg donepezil								
		01:00	09:00				X					
		02:00	10:00	240 mL fluid intake			X					
		03:00	11:00				X					
		04:00	12:00	240 mL fluid intake, Lunch ³			X		X	X	X	
		06:00	14:00				X					
		08:00	16:00				X					
		10:00	18:00	Dinner ³			X					
	12:00	20:00				X		X	X	X		
	2	18:00	02:00				X					
		24:00	08:00			X	X		X	X	X	
	3	48:00	08:00			X	X				X	
	4	72:00	08:00			X	X					X
		72:30	08:30	Discharge ¹¹				X ¹⁰	X	X	X	
	5	96:00	08:00	Ambulatory visit			X		X	X	X	
6	120:00	08:00	Ambulatory visit			X					X	
7	144:00	08:00	Ambulatory visit			X					X	
8	168:00	08:00	Ambulatory visit			X					X	
9	192:00	08:00	Ambulatory visit			X					X	
10	216:00	08:00	Ambulatory visit		X	X	X ¹⁰	X	X	X		
11	240:00	08:00	Ambulatory visit			X					X	
12	264:00	08:00	Ambulatory visit			X					X	
13	288:00	08:00	Ambulatory visit			X					X	
14	312:00	08:00	Ambulatory visit			X					X	
15	336:00	08:00	Ambulatory visit		X	X					X	

Visit ^{3,4}	Day	Planned time (relative to first drug administration [h:min])	Approximate clock time of actual day [h:min]	Event and comment	Safety laboratory	PK _{plasma} (BI 425809)	PK _{plasma} Donepezil	Safety assessments	12-lead ECG ¹⁴	Vital signs (BP, PR) ¹⁴	Questioning for AEs and concomitant therapy ⁶	

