9. C-SSRS
10. Neurological assessment (i.e. Romberg and Unterberger test, assessment of gait, further tests as needed) to be performed at the time points mentioned in the [Flow Chart](#) above and at any times CNS adverse events are reported
11. Discharge after confirmation of fitness by the investigator/designee
12. Safety laboratory to be taken within 3 days prior to first trial drug administration of Visit 2 and 3. All results must be available and be checked by the investigator or his/her designee before trial drug administration.
13. Colour discrimination, visual acuity testing, Amsler grid test: tests will be performed at screening, EOT and at any time visual adverse events are reported
14. All blood pressure measurements, as well as pulse rate and ECG will be measured after at least 5 minutes of rest in the supine position
15. Only urine drug screen and alcohol breath test and urine pregnancy testing (female subjects), no safety lab

** There is no wash-out period between Visit 2 and Visit 3. Day 1 of Visit 3 follows directly after day 15 of Visit 2 but these are different days

TABLE OF CONTENTS

TITLE PAGE	1
CLINICAL TRIAL PROTOCOL SYNOPSIS	2
FLOW CHART	4
TABLE OF CONTENTS	10
ABBREVIATIONS	14
1. INTRODUCTION.....	17
1.1 MEDICAL BACKGROUND	17
1.2 DRUG PROFILE	17
1.2.1 BI 425809	17
1.2.1.1 Non-clinical pharmacokinetics	17
1.2.1.2 Non-clinical safety pharmacology and toxicology	18
1.2.1.3 Clinical experience in humans	18
1.2.1.4 Clinical pharmacokinetics.....	19
1.2.2 Donepezil.....	20
1.2.3 Residual Effect Period	23
1.3 RATIONALE FOR PERFORMING THE TRIAL	23
1.4 BENEFIT - RISK ASSESSMENT	23
2. TRIAL OBJECTIVES AND ENDPOINTS.....	26
2.1 MAIN OBJECTIVES, PRIMARY AND SECONDARY ENDPOINTS	26
2.1.1 Main objectives.....	26
2.1.2 Primary endpoints	26
2.1.3 Secondary endpoint	26
2.2.2.2 Safety and tolerability	27
3. DESCRIPTION OF DESIGN AND TRIAL POPULATION.....	28
3.1 OVERALL TRIAL DESIGN AND PLAN	28
3.2 DISCUSSION OF TRIAL DESIGN, INCLUDING THE CHOICE OF CONTROL GROUP	28
3.3 SELECTION OF TRIAL POPULATION	29
3.3.1 Main diagnosis for trial entry	29
3.3.2 Inclusion criteria	29
3.3.3 Exclusion criteria	29
3.3.4 Withdrawal of subjects from treatment or assessments	31
3.3.4.1 Discontinuation of trial treatment	32

3.3.4.2	Withdrawal of consent to trial participation	33
3.3.4.3	Discontinuation of the trial by the sponsor	33
3.3.5	Replacement of subjects	33
4.	TREATMENTS	34
4.1	INVESTIGATIONAL TREATMENTS	34

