No subject was withdrawn from the study for safety reasons. There were no deaths or serious adverse events reported. All of the observed AEs were considered to be resolved. Given this information, the study drugs appeared to be well-tolerated and there were no safety concerns observed [[R15-4356](#)].
- A study to investigate the pharmacokinetic drug-drug interaction following oral administration of BI 409306 and donepezil in 32 healthy male (n = 17) and female (n = 15) subjects. Part 1 of this trial was performed as a one fixed sequence, open-label trial, in which single doses of BI 409306 and multiple doses of donepezil (5 mg qd for 7 days followed by 10 mg qd for 14 days) were administered, Part 2 of this trial was a randomised, open-label, 2-way crossover design, in which single doses of donepezil and multiple doses of BI 409306 were given.
In Part 1 of the trial, i.e. after multiple doses of donepezil, 16 out of 18 subjects (88.9%) were reported with at least 1 AE that was assessed as drug-related. The most frequently reported drug-related AEs were dizziness and nausea (both 55.6% of subjects), followed by headache and fatigue (both 22.2%). Dizziness was only observed after administration of donepezil alone, whereas nausea and headache were observed after administration of donepezil alone and in combination with BI 409306. As expected visual brightness a known AE of BI 409306 was only observed after BI 409306 administration. Fatigue was observed in all 3 treatment phases.
All subjects completed the trial except for 1 subject in Part 1 who withdrew during the second treatment period (donepezil administration) because of AEs that were considered not to be drug-related (lower abdominal pain, haematochezia, and ruptured ovarian cyst) [[c09564954](#)].

According to [[R15-4794](#), [R18-3913](#)], the safety profile mainly results from the cholinergic activity of donepezil, resulting in

- Gastrointestinal symptoms (e.g. nausea, diarrhea, vomiting, abdominal pain, gastric and duodenal ulcers and gastrointestinal hemorrhage)
- Cardiac symptoms (e.g. syncope, bradycardia, sino-atrial block, atrioventricular block)
- Central-nervous symptoms (e.g. syncope, dizziness, insomnia, seizures, extrapyramidal symptoms and neuroleptic malignant syndrome)

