1.2.3 Residual Effect Period

The Residual Effect Period (REP) of BI 425809 is 11 days, the REP for donepezil 15 days. This is the period after the last dose with measurable drug levels and/or pharmacodynamic effects is still likely to be present.

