7.3.4 Safety analyses

Safety will be analysed based on the assessments described in [Section 2.2.2.2](#). All treated subjects (TS, refer to [Section 7.2](#)) will be included in the safety analysis. Safety analyses will be descriptive in nature and based on BI standards. No hypothesis testing is planned.

For all analyses, the treatment actually administered (= treatment at onset) to the subject will be used (any deviations from the randomised treatment will be discussed in the minutes of the Report Planning Meeting).

Treatments will be compared in a descriptive way. Tabulations of frequencies/proportions will be used to evaluate categorical (qualitative) data, and tabulations of descriptive statistics will be used to analyse continuous (quantitative) data.

Measurements (such as vital signs, or laboratory parameters) or AEs will be assigned to treatments (see [Section 4.1](#)) based on the actual treatment at the planned time of the measurement or on the recorded time of AE onset (concept of treatment emergent AEs). Therefore, measurements planned or AEs recorded prior to first intake of trial medication will be assigned to the screening period, those between first trial medication intake and end of REP (see [Section 1.2.3](#)) will be assigned to the treatment period. Events occurring after the REP but prior to next intake or end of trial termination date will be assigned to 'follow-up'. In case of two or more treatments, the follow-up will be summarized according to the previous treatment. These assignments including the corresponding time intervals will be defined in detail in the TSAP. Note that AEs occurring after the last per protocol contact but entered before final database lock will be reported to Pharmacovigilance only and will not be captured in the trial database.

Additionally, further treatment intervals (analysing treatments) may be defined in the TSAP in order to provide summary statistics for time intervals, such as combined treatments, on-treatment totals, or periods without treatment effects (such as screening and follow-up intervals).

Adverse events will be coded using the Medical Dictionary for Regulatory Activities (MedDRA). Frequency, severity, and causal relationship of AEs will be tabulated by treatment, system organ class, and preferred term. SAEs, AESIs (see [Section 5.2.7.1](#)), and other significant AEs (according to ICH E3) will be listed separately.

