6.6 HANDLING OF MISSING DATA AND OUTLIERS

Data of screened subjects who were withdrawn from the trial prior to first administration of any study drug will not be reported in the CTR.

Data of subjects who failed to complete all periods of the study (dropouts or withdrawals) will be reported in the CTR as far as their data are available. All withdrawals will be documented and the reason for withdrawal reported in the CTR.

CTP: It is not planned to impute missing values for safety parameters.

One exception where imputation might be necessary for safety evaluation are AE dates. Missing or incomplete AE dates are imputed according to BI standards (3).

Missing data and outliers of PK data are handled according to BI standards (4) and (5).

CTP: PK parameters that cannot be reasonably calculated based on the available drug concentration-time data will not be imputed.

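### SAP Tables 6.1: 3 and 6.1: 4 leave on-treatment safety phases without an end for subjects who stop before a boundary dose, and overlap follow-up after a last BI 425809 dose on Part 2 Days 10–13

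*SAP*

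**What the plan says.** SAP Section 6.1 defines, separately for each part, the analysis phases for adverse events, vital signs, safety laboratory data and visual tests. Section 7.8.1 sends every adverse event through these tables, and Section 7.2 uses the phases to decide which medication is concomitant.

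Three on-treatment intervals end only at a later planned dose:

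- 'BI part 1' ends at the first donepezil dose.
- 'Don part 1' has two sub-phases, with ends "First phase: Date/time of second administration of BI 425809 Second phase: Date/time of last administration of donepezil + 15*24h".
- 'BI part 2' likewise: "Combination of two phases: First phase: Date/time of second administration of donepezil Second phase: Date/time of last administration of BI 425809 + 11*24h".

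In both two-part phases the alternative end at trial termination follows the second sub-phase only. Final follow-up starts at last donepezil + 15 days in Part 1 and at last BI 425809 + 11 days in Part 2.

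On early stoppers, SAP Section 6.6 states: "Data of subjects who failed to complete all periods of the study (dropouts or withdrawals) will be reported in the CTR", as far as available. Protocol Section 3.3.4 asks that they be questioned about adverse events at or after the end of the residual effect period (REP) where possible. Protocol Section 7.3.4 gives a general rule, under which the treatment period takes events described as "those between first trial medication intake and end of REP", and leaves the detailed intervals to the SAP.

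**The concern.** The limits presuppose that the boundary doses are given. If one is not, the tables state no end for an interval that has already started, and the REP rule of Protocol Section 7.3.4 is not carried over as a fallback. A second fault needs no missing dose: final follow-up in Part 2 depends only on the last BI 425809 dose, yet the combination phase runs on the longer donepezil REP.

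The main adverse event tables (CTR Section 15.3) show on-treatment phases only. Whether an event of an early stopper appears there, and under which treatment label, therefore depends on a rule that the SAP does not state.

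**Working it through.** **Inputs** (day 0 = first dose of the part)

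- REPs, Protocol Section 1.2.3: "The Residual Effect Period (REP) of BI 425809 is 11 days, the REP for donepezil 15 days".
- Part 1, flow chart note: "Day 1 of Visit 3 follows directly after day 8 of Visit 2". Visit 3 Day d is therefore day 7 + d, and first donepezil is day 8. From SAP Table 6.1: 1, second BI 425809 (Visit 3 Day 22) is day 29 and last donepezil (Day 28) is day 35.
- Part 2, flow chart note: "Day 1 of Visit 3 follows directly after day 15 of Visit 2". Visit 3 Day d is therefore day 14 + d, and first BI 425809 is day 15. From SAP Table 6.1: 2, second donepezil (Day 10) is day 24 and last BI 425809 (Day 24) is day 38.

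**Step 1. Completers: reproduce the SAP's planned durations**

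| Phase | Intervals (days) | Length | SAP |
|---|---|---|---|
| BI part 1 | 0–8 | 8 | 8 |
| Don part 1 | 11–29, 40–50 | 18 + 10 = 28 | 28 |
| Don + BI part 1 | 8–11, 29–40 | 3 + 11 = 14 | 14 |
| Don part 2 | 0–15 | 15 | 15 |
| BI part 2 | 15–24, 39–49 | 9 + 10 = 19 | 19 |
| BI + Don part 2 | 24–39 | 15 | 15 |

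Here 40 = 29 + 11, 50 = 35 + 15, 39 = 24 + 15 and 49 = 38 + 11. All six figures agree, so the tables are being read as intended.

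**Step 2. Part 1, last donepezil on Visit 3 Day d, d = 1 to 21, no second BI 425809 dose**

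'Don part 1' starts at day 11. Its first end and its second start are both missing. Follow-up starts at (7 + d) + 15 = day 22 + d. The stretch with no closed interval is (22 + d) − 11 = d + 11 days: 12 days for d = 1, 21 for d = 10, 32 for d = 21. If the missing end is read as open, every event after day 22 + d falls in both 'Don part 1' and follow-up.

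**Step 3. Part 1, donepezil never taken**

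'BI part 1' runs from day 0 with no end. 'Don part 1' still starts at day 0 + 11 = 11, because its start is tied to BI 425809. Follow-up has no start, because it is tied to a donepezil dose.

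**Step 4. Part 2, BI 425809 stopped on Day d, d = 1 to 9, no second donepezil dose**

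'BI part 2' starts at day 15 with no end. Follow-up starts at (14 + d) + 11 = day 25 + d. The stretch with no closed interval is d + 10 days: 11 for d = 1, 15 for d = 5, 19 for d = 9.

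**Step 5. Part 2, last BI 425809 on Day 10 to 13**

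All dates exist. 'BI + Don part 2' ends at day 39; follow-up starts at day 25 + d.

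| Last BI day | Follow-up starts | Overlap = 39 − (25 + d) | Second 'BI part 2' sub-phase |
|---|---|---|---|
| 10 | 35 | 4 days | starts 39, ends 35 |
| 11 | 36 | 3 days | starts 39, ends 36 |
| 12 | 37 | 2 days | starts 39, ends 37 |
| 13 | 38 | 1 day | starts 39, ends 38 |

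**Step 6. Where the tables still work**

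- Part 1, last donepezil on Day 22: 'Don part 1' is 11–29 and 40–44, with follow-up from 44. Later stops behave the same way.
- Part 2, last BI 425809 on Day 14: follow-up starts at day 39, exactly where the combination phase ends. Later stops are also consistent.
- Part 2, BI 425809 never taken: 'Don part 2' closes at day 15; only the end of the first follow-up sub-phase is missing.

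**The case against.** The strongest reply is that the intent can be recovered. Protocol Section 7.3.4 treats time up to the end of the REP as treatment and later time as follow-up; SAP Section 4 declares accordance with the protocol; and the follow-up row dates its own start whenever at least one donepezil dose (Part 1) or BI 425809 dose (Part 2) was given. For the Day 10 example in Part 1, the sensible reading is donepezil until day 32. That stands as a guide to intent. But the protocol delegates the intervals to the SAP, and in the Day 10–13 case the SAP's explicit rules give two phases at once.

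SAP Section 6.1 also refers technical implementation to an ADS Plan that is not available here and may hold a rule for dropouts. That is a real limit, although the definition belongs in the SAP. The table layout was flattened in extraction, so the termination cap might apply to both sub-phases. That would close the open intervals of 'Don part 1' and 'BI part 2' but leave them overlapping follow-up for anyone followed past the REP.

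A reader might infer more than the documents support:

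- *That every early stopper is affected.* Step 6 shows otherwise, and events in intervals already closed are safe. In Part 1, onset on Visit 3 Days 1–3 lies in the closed combination interval, days 8–11.
- *That adverse event rates for the single drugs are biased.* No direction or size can be derived. The tables are descriptive, individual values are listed, and withdrawals are reported with reasons.
- *That the Day 10–13 overlap inflates the main tables.* CTR Section 15.3 omits follow-up, so the event appears there only under the combination. The overlap also begins 11 days after the last BI 425809 dose, so it is unlikely to contain the event that caused the stop.

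**Conclusion.** The point holds within these limits. The phase definitions fail for Part 1 subjects who stop before Visit 3 Day 22 and for Part 2 subjects whose BI 425809 stops on Days 1–9. Separately, because of the unequal REPs, they double-assign 4 to 1 days for a last BI 425809 dose on Part 2 Days 10–13. Safety data of these subjects can be unassigned, double-assigned or mislabelled. The PK analysis is unaffected.

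The likely number is small. In the sponsor's earlier donepezil interaction trial (Protocol Section 1.2.2), 1 of 18 Part 1 subjects withdrew, during donepezil dosing and for events judged not drug-related. Assuming the same rate and a stop before the boundary dose, 18 × 1/18 = 1 subject in Part 1. Many more could be affected only if the sponsor ended the trial early under Protocol Section 3.3.4.3 with a whole cohort still short of Day 22. The conclusion assumes that the unseen ADS Plan holds no rule that settles these cases.

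**What to change.** Amend SAP Tables 6.1: 3 and 6.1: 4 as follows.

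1. Create a phase or sub-phase only if the drug or drugs defining it were taken and its start precedes its end. One whose starting dose was not given is not created.
2. End 'BI part 1' and the first sub-phases of 'Don part 1' and 'BI part 2' at the earliest of: the boundary dose, if given; the last dose of that phase's drug plus its REP (11*24h or 15*24h); and the trial-termination cap.
3. Keep 'BI + Don part 2' running to second donepezil + 15*24h, capped at trial termination.
4. Start final follow-up at the latest REP end among the drugs actually received. Keep the existing first 'F/U part 2' sub-phase between first donepezil + 15*24h and the first BI 425809 dose.

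Check of the result, in days from first dose:

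- Part 1, last donepezil Day 10: BI 0–8, Don + BI 8–11, Don 11–32, follow-up from 32.
- Part 1, no donepezil: BI 0–11, follow-up from 11.
- Part 2, last BI 425809 Day 5: Don 0–15, BI 15–30, follow-up from 30.
- Part 2, last BI 425809 Day 12: Don 0–15, BI 15–24, BI + Don 24–39, follow-up from 39.

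The cost is wording in two tables and the matching derivation code. No new data are needed, and the phases of completers do not change.
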